### 4.1.2. Secondary outcomes:

[figure not shown]
- Offspring
  - Time to birth
    - Preterm birth before 37 weeks: rate of delivery before 36+6 weeks
    - Preterm birth before 34 weeks: rate of delivery before 33+6 weeks
    - Preterm birth before 32 weeks: rate of delivery before 31+6 weeks
    - Preterm birth before 30 weeks: rate of delivery before 29+6 weeks—
    - Preterm birth before 28 weeks: rate of delivery before 27+6 weeks—
  - Birth weight: median weight (g) of the newborns at birth
  - Fetal or neonatal death: rate of intrauterine demise or neonatal death during the first 24 hours
  - Neonatal morbidity: rate of major adverse neonatal outcomes before discharge from the hospital
    - Intraventricular Haemorrhage (IVH): grades III-IV
    - Retinopathy of prematurity
    - Respiratory Distress Syndrome (RDS): grades II-IV,
    - Need for ventilation > 72 h
    - Necrotising enterocolitis
    - Proven or suspected sepsis, antibiotics (>5 days)
    - Need (Duration in days) for neonatal special care (NICU)
  - Harm from intervention
- Mother:
  - Maternal death
  - Significant maternal adverse events (rate):
    - Heavy bleeding: bleeding that requires a medical intervention
    - Cervical tear: cervical rupture due to the pessary placement
    - Uterine rupture: rupture of the uterus due to contractions or surgery
  - Physical or psychological intolerance to pessary: discomfort or pain due to the pessary that makes daily life uncomfortable (number of cases)
  - Rupture of membranes before 32 weeks: rate of—rupture of amniotic membranes before 31+6 weeks
  - Infection/inflammation
  - Hospitalisation for threatened preterm labour before 32 weeks: requirement of hospitalisation due to preterm contractions that need medical treatment to try to stop them before 31+6 weeks (rate)

- Mean hospital stay duration: number of days of admittance at the hospital
- Use of tocolytic treatment: Type of tocolytic, days of treatment, dose

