#### 4.3. Flowchart.

#### 4.4. Description of the medical device and the treatment regimen.

The cervical pessary is a vaginal device (silicone ring) that is used to treat pregnant women for preventing spontaneous preterm birth. This device can be easily placed around the uterine cervix without pain (see annex I).

Women with a singleton pregnancy at 12+0 – 18+0 weeks of gestation and a history of at least one previous preterm delivery before 34+0 weeks and/or a history of late abortion attending the reference hospital for a preventive examination will be informed of the ongoing trial. The patient will be advised of the intended therapeutic effect and possible side effects. If they agree and after obtaining their informed consent, they will be randomised according to either progesterone (=control group) or cervical pessary placement up to 37+0 weeks (= pessary group).

If the pregnant woman is assigned to the pessary group and after having excluded a vaginal infection the pessary will be inserted directly. This procedure does not need anaesthesia and it does not need to be done in a surgery room. After the insertion of the pessary the correct fit of the pessary is verified by transvaginal ultrasound and in case it does not fit perfectly, it can easily be adjusted.

In the control-group, the pregnant women be treated with progesterone. Utrogestan is one of the normal drugs in China to prevent spontaneous preterm birth, the Utrogestan used in this study is from Laboratories Besins International. For the enrollment, pregnant women in the control group were treated by 200 mg QN, it is used for 34 gestational weeks.

The pessary will be removed at 37+0 weeks of gestation, or before if any unexpected event occurs (see 4.6). After insertion of the pessary the obstetrical management during the remainder of the pregnancy will be usual management.

Further surveillance of the pregnancy will not be influenced by the participation on the study.

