#### **4. 10. 4. Rescue treatment criteria.**

According the current guide and expert advice, when the routine follow-up examination, the rescue cervical cerclage may be adopted when the secondary cervical shortening occurs.

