## **7. Statistics**

### **7.1. Description of statistical methods.**

A descriptive analysis by preterm birth will be carried out calculating means and medians for quantitative variables and proportions for categorical variables.

Two-sided Z-tests will be used for comparing among exposure and outcomes groups per pregnancy. A multivariate logistic regression will be fitted to control for possible confounders. Relative risks and 95% confidence interval will be calculated for the outcomes.

All analysis will be carried out with SPSS® 19.0 statistical package (IBM Company SPSS Inc. Headquarters, Chicago, Illinois. USA). Statistical significance will be accepted in all cases with a  $p < 0.05$ .

Outcome	Statistical Test
Birth before 34 Weeks of Gestation	Two-sided Z-Test (RR, 95% CI)
Time to Birth	Log-rank test (HR, 95% CI)
Birthweight	Multilevel model (mean $\pm$ SD)
Fetal / Neonatal Death	Two-sided Z-Test (RR, 95% CI)
Neonatal Morbidity	Two-sided Z-Test (RR, 95% CI)
Need for Hospitalization	Two-sided Z-Test (RR, 95% CI)
Days of Hospitalization	Two-sided Z-Test (RR, 95% CI)
Maternal Adverse Events	Two-sided Z-Test (RR, 95% CI)
Pessary Intolerance	Two-sided Z-Test (RR, 95% CI)
Vaginal Infections	Two-sided Z-Test (RR, 95% CI)

the complete data set for the secondary endpoints will be available after the last women enrolled in this study has given birth, so the analysis of these outcome parameter will be done right after this event.

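### Cervical tear is defined by a cause that only the pessary arm can have, yet it sits in a maternal adverse event rate that is compared between arms

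*Protocol*

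**What the plan says.** Protocol Section 4.1.2, under the mother's secondary outcomes, names three significant maternal adverse events, to be reported as a rate. Two of them mention no device: the first entry, "Heavy bleeding: bleeding that requires a medical intervention", and the last entry, "Uterine rupture: rupture of the uterus due to contractions or surgery". The middle entry does mention one: "Cervical tear: cervical rupture due to the pessary placement".

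Maternal death and intolerance to the pessary are separate items in the same list. Intolerance is given as a number of cases.

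Section 4.4 states that women are "randomised according to either progesterone (=control group) or cervical pessary placement up to 37+0 weeks (= pessary group". Section 2.2 describes the control strategy as usual management with rescue cerclage if the cervix shortens. Section 4.10.4 says that "the rescue cervical cerclage may be adopted when the secondary cervical shortening occurs", without limiting this to one arm.

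The test table in Section 7.1 has a row for "Maternal Adverse Events" with a two-sided Z-test, relative risk and 95% confidence interval. Section 7.4 analyses all randomised women. Section 5.3 has all adverse events recorded on the CRF, attributed or not, with an assessment of relatedness.

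**The concern.** The cause is written into the definition of one component, and only one arm is exposed to that cause. A control woman whose cervix ruptures through a cerclage suture or in labour has no event under this definition. The other two components name no device and can occur in either arm.

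At stake is what the maternal safety comparison can say about cervical injury. The control strategy can itself involve a procedure on the cervix. As defined, the outcome cannot show harm from that procedure in controls, and it cannot show the pessary strategy as equal to or safer than control once a single pessary-attributed rupture is recorded.

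**Working it through.** **Who can have the event**

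| Component | Pessary arm | Control arm |
|---|---|---|
| Heavy bleeding | possible | possible |
| Uterine rupture | possible | possible |
| Cervical tear | possible, if due to the pessary | impossible without a pessary |

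The last cell holds unless a control woman is given a pessary, which the protocol does not provide for. The relative risk (pessary over control) for this component then has a zero denominator at any true tear rate.

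**Inputs for scale.** The arm size of 121 is from Section 7.2. The Z-test with pooled variance and the 5% two-sided level are from Sections 7.1 and 7.2. The arm size reproduces: with 0.924 against 0.80, the average proportion is 0.862 and

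n = [1.96 × √(2 × 0.862 × 0.138) + 0.842 × √(0.924 × 0.076 + 0.80 × 0.20)]² / 0.124² ≈ 120.3, so 121, with power 0.802.

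The protocol states no cervical tear rate, so there is no figure of its own to reproduce on this point.

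**Z-test with control fixed at zero.** With x counted tears in the pessary arm, the pooled proportion is x/242 and

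z = (x/121) / √[(x/242)(1 − x/242)(2/121)] = √x / √(1 − x/242).

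- x = 3: 1.732 / √(1 − 3/242) = 1.74, not significant
- x = 4: 2 / √(1 − 4/242) = 2.02, significant at 5%

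**Illustration under assumed rates.** Suppose the true all-cause tear rate t is the same in both arms, so that the true relative risk is 1, and a share s of pessary-arm tears is attributed to the pessary. The counted number X is binomial(121, s·t), and the test on this component is significant when X ≥ 4.

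| t (assumed) | Expected tears per arm, all causes | P(significant), s = 0.5 | P(significant), s = 1 |
|---|---|---|---|
| 1% | 1.2 | 0.3% | 3.4% |
| 2% | 2.4 | 3.4% | 22% |
| 5% | 6.1 | 36% | 86% |
| 10% | 12.1 | 86% | 99.9% |

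Every one of these rejections is against the pessary.

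**Pooled rate.** Suppose instead that the three components are pooled, with a common rate a for the other two and no overlap (assumption). The recorded rates are a + s·t in the pessary arm and a in control, so the recorded relative risk is 1 + s·t/a where the truth is 1. At t = 2% and s = 0.5 the artificial excess is 0.02 × 0.5 = 1 percentage point, or 1.2 women of 121.

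**The case against.** The strongest defence is that recording device-attributed harm is legitimate and visibly intended. Section 4.1.2 also lists intolerance to the pessary, and Section 7.1 gives that item the same test. On this view cervical tear is a device-safety count, and the only slip is giving it a between-arm relative risk. Part of this stands: a pessary-specific count is worth having. But cervical tear sits inside the compared rate, not beside intolerance. Even with perfect attribution, a count of pessary-caused ruptures cannot be set against ruptures caused by rescue cerclage in the control strategy.

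Second, Section 5.3 puts all adverse events on the CRF with relatedness, so control-arm ruptures should be on record. This stands, and it confines the problem to the named outcome and its test. It does not remove it: redefining the outcome once data have been seen in an open trial would be post hoc.

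Third, the illustration depends on tear rates that the protocol does not give. This stands. At 1% to 2% with half attributed, the false-positive chance is 0.3% to 3.4%, below the nominal 5%, although all of it lies on one side. Section 7.1 also does not say whether the components are tested singly or pooled.

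A reader might go further in three ways that the documents do not support:

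- That the whole maternal safety comparison is biased. Only one of the three components is affected, and a control-arm tear whose bleeding needed intervention would still count as heavy bleeding.
- That a tear in labour with the pessary in place drops out because it did not happen at insertion. Sections 4.2 and 4.4 use placement for the whole pessary treatment, so a device-caused tear counts whenever it occurs. What remains is a judgement about cause by staff who know the arm.
- That the definition biases the comparison equally in both directions. It sets controls to zero, so the recorded contrast can never favour the pessary. Cautious attribution in the pessary arm may shrink the recorded excess, but that comes from the attribution and not from the definition.

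**Conclusion.** The point holds for cervical tear and for any pooled maternal adverse event rate that includes it. The component is zero in controls by definition and can count only against the pessary. This follows from the wording alone and needs no assumed rate.

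The size of the bias cannot be stated. The test thresholds (three counted tears not significant, four significant) rest only on 121 per arm and the planned test. The false-positive probabilities rest on assumed equal all-cause rates and an assumed attribution share, and the high ones need rates of 5% to 10% that nothing in the protocol supports.

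This is one component of a secondary safety outcome. It does not touch the primary outcome, maternal death, heavy bleeding or uterine rupture. It should still be corrected, because the rule is stated, the result is one-sided, and the repair is cheap.

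**What to change.** In Section 4.1.2, delete the clause that ties cervical tear to the pessary. Define the event identically in both arms and keep its severity level: cervical rupture from randomisation to the end of the delivery admission, whatever the cause. Do not widen it to any laceration, since minor delivery tears in both arms could dilute a real signal.

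Use the relatedness information already collected under Section 5.3 to report pessary-attributed ruptures as a descriptive count in the pessary arm only, with no between-arm test.

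The cost is one changed definition. The small downside is that ruptures in labour unrelated to treatment are counted, in both arms alike. Detection and attribution by unblinded staff remain, but attribution would no longer decide whether an event enters the comparison.

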## **2.2. Description of the study population.**

Women with a singleton pregnancy at 12 – 18 weeks of gestation and a history of at least one previous preterm delivery before 34+0 weeks and/or a history of late abortion attending the reference hospital and who do not fulfil the exclusion criteria the study will be proposed. The patients will be informed of the intended therapeutic effect and possible side effects. If they agree and after obtaining their informed consent, they will be randomised according to either usual management with rescue cerclage placement only when (and as soon as possible) a cervical shortening below 25 mm occurs (=control group) or cervical pessary placement (= pessary group). Pessaries or cerclage shall be placed up to 37+0 weeks of gestation. Serial cervical length measurements shall be conducted every 4 weeks in order to diagnose cervical shortening as soon as possible in the control group.

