#### **4.6. Completion and interruption criteria of the study or the subjects.**

The pessary will be removed at 37+0 weeks of pregnancy. The indications to remove them before this time will be: active bleeding stronger than period bleeding, persistent contractions after tocolysis and premature rupture of the membranes after 34+0 weeks.

After removing the pessary, the obstetrical management will be done as usual and will not be influenced by the study.

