#### **4.11. Treatment of Subjects**

##### **4.11.1. Treatments to be administered.**

The pessary will be inserted during a preventive examination in pregnancy in the examination room. This procedure does not need anaesthesia and it does not need to be done in a surgery room. After the insertion of the pessary the correct fit of the pessary is verified by transvaginal ultrasound and in case it does not fit perfectly, it can easily be adjusted. pregnant women in the control group were treated by 200 mg QN, it is used for 34 gestational weeks. The pessary or cerclage will be removed at 37+0 weeks of gestation, or before if any unexpected event occurs (see 4.6).

After insertion of the pessary the obstetrical management during the pregnancy will be usual management.

Further surveillance of the pregnancy will not be influenced by the participation on the study.

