### **5.3. Procedures for immediate notification of serious or unexpected adverse events.**

All AEs occurring during the study /or observed by the investigator or reported by the participant, whether or not attributed to study medication, will be recorded on the CRF.

The following information will be recorded: description, date of onset and end date, severity, and assessment of relatedness to study medication, other suspect drug or device and action taken. Follow-up information should be provided as necessary.

AEs considered related to the sanitary device, as judged by a medically qualified investigator, will be followed until resolution or the event is considered stable. All related AEs that result in a participant's withdrawal from the study or are present at the end of the study, should be followed up until a satisfactory resolution occurs.

It will be left to the investigator's clinical judgment whether or not an AE is of sufficient severity to require the participant's removal from treatment. A participant may also voluntarily withdraw from treatment due to what he or she perceives as an intolerable AE. If either of these occurs, the participant must undergo an end of study assessment and be given appropriate care under medical supervision until symptoms cease or the condition becomes stable.

A medically qualified investigator will assess the relationship of AEs to the study medication.

All SAEs must be reported to the main investigator. He will perform an initial check of the report, request any additional information, and he will notify it to the Ethics Committee and CFDA. All SAE information will be recorded. It may be appropriate that some SAEs do not require immediate reporting but this must be justified. Justification might be determined, for example, by admission to hospital, or prolongation of hospitalization, where this is to be expected in the underlying disease or condition.

All adverse events (AE) life-threatening or resulting in death will be notified within 24 hours. All AE that are not life-threatening will be notified within 15 days. The rest of AE will be recorded and analyzed at the end of the study.

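### Membrane rupture is compared between arms only before 32 weeks although the pessary is worn to 37+0; add a rate before 37+0, and correct the 34+0 removal mark in the visit schedule

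*Protocol*

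**What the plan says.** **Outcome.** Among the maternal outcomes, Protocol section 4.1.2 gives "Rupture of membranes before 32 weeks: rate of" membrane rupture, with the limit written as before 31+6. No other listed outcome counts membrane rupture.

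**Device wear.** Section 2.2 has "Pessaries or cerclage shall be placed up to 37+0 weeks of gestation", and section 4.11.1 has "The pessary or cerclage will be removed at 37+0 weeks of gestation". Section 4.4 states 37+0 twice and section 4.6 once, which makes five statements in four sections.

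**Early removal.** Section 4.6 lists three reasons to take the pessary out before 37+0. One is "premature rupture of the membranes after 34+0 weeks".

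**Analysis.** The section 7.1 table has a row "Maternal Adverse Events" but none for membrane rupture. In section 4.1.2 the matching item lists heavy bleeding, cervical tear and uterine rupture.

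**General safety recording.** Section 5.3 puts all adverse events on the case report form. For those not notified early it says "The rest of AE will be recorded and analyzed at the end of the study".

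**Schedule.** The section 6.2 table has three time columns: inclusion at 12+0 to 18+0, a visit at 34+0, and a postnatal evaluation. The row for pessary or cerclage removal is marked under 34+0.

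**The concern.** The protocol provides for membrane rupture in the last weeks of wear, since it tells sites to remove the pessary when that happens. Yet the one outcome that compares rupture between the arms stops before those weeks begin. The whole period of the removal rule, 34+0 to 37+0, lies outside it. Rupture at 32+0 to 33+6 is neither counted by the outcome nor a listed removal reason.

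The rupture result would therefore speak only to the period before 32 weeks. A reader asking how often membranes ruptured in each arm while the device was still in place would find no defined rate for the later weeks. The primary outcome and the sample size are not affected.

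The schedule raises a separate question of conduct. A site that works from the table would remove the pessary at 34+0, against the text.

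**Working it through.** **1. The plan's own figure.** The protocol gives no number for membrane rupture. The only stated figure used here is 121 per arm (section 7.2: 0.924 against 0.80, two-sided 5%, 80% power, pooled Z test).
- Mean proportion: (0.924 + 0.80)/2 = 0.862.
- n = [1.960 × √(2 × 0.862 × 0.138) + 0.842 × √(0.924 × 0.076 + 0.80 × 0.20)]² / 0.124² = (0.956 + 0.404)² / 0.015376 ≈ 120.3, so 121 per arm. The figure reproduces, with power 80.2%.

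**2. Device weeks outside the rupture outcome.** Insertion is at 12+0 to 18+0 (section 4.10.1) and planned removal at 37+0.
- Planned wear: 37 − 12 = 25 weeks, or 37 − 18 = 19 weeks.
- Not covered: 37 − 32 = 5 weeks.
- Share: 5/25 = 20%; 5/19 = 26.3%.

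These shares apply to a woman who reaches 37+0 with the pessary in place. With earlier delivery the uncovered share is smaller. They are shares of weeks and not of ruptures.

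**3. Does another listed item close the gap?**
- The maternal adverse event row in section 7.1 most naturally refers to the item of that name in section 4.1.2, whose list omits membrane rupture.
- Harm from intervention (section 4.1.2) is undefined and sits under the offspring outcomes.
- Birth before 34 and before 37 weeks reflects some late ruptures, but mixed with deliveries from other causes.
- Hospital stay and tocolytic use have no gestational limit, but neither counts ruptures.
- Adverse event recording captures the events but defines no rupture rate by arm.

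**4. Precision of an added rate.** The protocol gives no rupture rates, so the rates below are assumptions, taken as equal in both arms with 121 women each. SE(log RR) = √[2(1 − p)/(121p)], and the 95% CI around RR 1.0 is exp(±1.96 × SE).

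| Assumed rate p | Expected events per arm | SE(log RR) | 95% CI around RR 1.0 |
|---|---|---|---|
| 2% | 2.4 | 0.900 | 0.17 to 5.84 |
| 5% | 6.1 | 0.560 | 0.33 to 3.00 |
| 10% | 12.1 | 0.386 | 0.47 to 2.13 |
| 15% | 18.1 | 0.306 | 0.55 to 1.82 |

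**5. Why the later window should be descriptive.** A woman must still be pregnant to have a late rupture. Suppose, as an assumption, that the section 7.2 proportions mean still pregnant at 34 weeks; that section names no outcome. With identical rupture risk among women still pregnant, the RR from 34 weeks on over all randomised women would be 0.924/0.80 = 1.155, with no true difference in risk.

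**6. The schedule.** The text gives 37+0 five times; the table as it reads gives 34+0.
- Difference: 37 − 34 = 3 weeks.
- Share of planned wear: 3/25 = 12%; 3/19 = 15.8%.
- Even if removal at 34+0 were intended, 34 − 32 = 2 weeks of wear would stay outside the rupture outcome. Step 2 therefore does not depend on the table.

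**The case against.** The strongest reply is that nothing here is an error. An outcome window need not equal the time a device is worn, and hospitalisation for threatened labour uses the same 32-week cut. Section 4.6 is a management rule, not an outcome definition, and it does not say that late rupture is expected. This stands: the 32-week rate should be kept.

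Second, the data are collected anyway. Adverse events are recorded without a gestational limit (section 5.3), and a late rupture that needs admission meets the serious adverse event definition (section 5.2). This also stands. A reader might infer that late ruptures are lost, and the protocol does not support that. What is missing is a defined rate by arm.

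Third, the added rate will be imprecise, and it is not free of the effect in step 5: if the pessary prolongs pregnancy, more women in that arm remain at risk of rupture before 37+0. This stands as a limit on interpretation. It argues for an estimate read beside the birth rates, not for leaving the rate out.

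Fourth, several rows of the section 6.2 table carry no marks, although section 4.4 calls for transvaginal ultrasound and exclusion of vaginal infection at insertion. The table may not show its full layout. The schedule point is therefore conditional on the original. It is still a contradiction as the table reads, because the removal mark sits under a clear 34+0 column and there is no column for 37+0.

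**Conclusion.** The point holds as a small safety-reporting gap. The defined rupture comparison leaves out up to 5 of 19 to 25 planned device weeks (20% to 26%) for a woman who reaches 37+0, including the whole period in which rupture is a stated reason for removal.

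Two stronger readings are tempting and not supported:
- That a fifth to a quarter of ruptures go uncounted. The share is of weeks, and the number of omitted ruptures cannot be estimated from the protocol.
- That the section 7.2 proportions show how many women come under the section 4.6 rupture rule. That rule concerns removal of a pessary, so it cannot apply to controls, and section 7.2 does not say what its proportions measure.

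The schedule conflict is separate and does not add weight to the rupture point. If the original table confirms it, a site following the table would end the intervention three weeks early (12% to 16% of planned wear).

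**What to change.** In section 4.1.2:
- Keep the 32-week rate but word the limit as before 32+0. Read literally, before 31+6 leaves out day 31+6.
- Add rupture of membranes before 37+0, ascertained in the same way in both arms from delivery records. Report it over all randomised women by randomised arm, with RR and 95% CI, as a safety estimate and not a test. Read it beside the rate of birth before 37 weeks.
- Give counts for 32+0 to 36+6 by arm, descriptively.
- Report the number of pessaries removed because of rupture.

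Add one row to the section 7.1 table.

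Separately, check the original section 6.2 table and correct the removal entry to 37+0.

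The cost is low. Women are followed to delivery even after withdrawal or removal (section 4.10.3), and the timing of rupture is already needed in both arms to apply the 32-week cut. No extra women, visits or alpha are required. The downside is one more imprecise secondary estimate, and the later window may hold only a few events per arm.
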